10.3.6 Primary Outcome and Methodology

Response criteria will be adapted from the International Working Group for AML, as stated in section 9.1.

10.3.7 Efficacy Analysis

The primary end-point is overall response rate (detailed in section 9.1). Descriptive statistics will be presented for all categories of each best response category. Duration of response and PFS will be listed and additionally summarized using Kaplan-Meier methodology. In addition, if at any time unacceptable toxicity is encountered in more than 33% of patients the accrual will stop and lower doses may be investigated.

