- 1. For patients with active relapse and given as reinduction, 200mg/m²/day divided in three doses daily (preferably every eight hours), taken orally at least 30 minutes pre or post meal. Patients will complete a daily diary to record the date, time and amount (number of tablets) of crenolanib taken and eating schedule. (Appendix III) Concurrent hydroxyurea (maximum 5g total daily dose) is permitted for the first 14 days of study therapy.
- 2. For patients continuing therapy as maintenance after allogeneic stem cell transplant (HSCT), the same dose of crenolanib most recently tolerated by the patient during induction will be restarted. Patients will complete a daily diary to record the date, time and amount (number of tablets) of crenolanib taken and eating schedule (Appendix III)

Planned Duration of Treatment:

The anticipated duration of patient involvement is a minimum of 28 days with a maximum of 365 days but assessed individually for each patient. Subjects will take crenolanib besylate daily as reinduction and may resume as maintenance after allogeneic stem cell transplant, until their disease has progressed, the patient has died, or the patient discontinues for adverse events, investigator's judgment, or other reasons.

Subjects who have discontinued will continue to be followed 30-days post last dose.

Reference Therapy, Dose and Mode of Administration:

No comparators will be used.

Criteria for Evaluation:

International Working Group for AML (Cheson, et. al., JCO, 2003)

Statistical Methods:

Protocol: ARO-004

The primary end-point is overall response rate. Descriptive statistics will be presented for all categories of each best response category. Duration of response and PFS will be listed and additionally summarized using Kaplan-Meier methodology. In addition, if at any time unacceptable toxicity is encountered in more than 33% of patients, the accrual will stop and lower doses may be investigated.

4. Abbreviations and Definitions

Adverse Event (AE)

Any untoward medical occurrence in a patient or clinical investigation subject administered a pharmaceutical product and which does not necessarily have a causal relationship with this treatment. An adverse event can therefore be any unfavorable and unintended sign (including an abnormal laboratory finding), symptom, or disease temporally associated with the use of a medicinal (investigational) product, whether or not related to the medicinal (investigational) product.

Audit

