6.3 Discontinuations

6.3.1 Discontinuations of Patients

The criteria for enrollment must be followed explicitly. If a patient who does not meet enrollment criteria is inadvertently enrolled, that patient should be immediately discontinued from the study drug unless specific approval is obtained from the IRB.

In addition, patients will be discontinued from the study drug but continued to be followed for survival data in the following circumstances:

- The patient experiences unacceptable toxicity as defined in Section 8.7 The patient is non-compliant (see Section 8.10).
- The investigator decides that the patient should be withdrawn, for example due to intercurrent illness that would, in the judgment of the investigator, affect assessments of clinical status to a significant degree. If this decision is made because of a serious adverse event or a clinically significant laboratory value, the study drug is to be discontinued and appropriate measures are to be taken. AROG or its designee is to be alerted immediately (see Section 11.1).
- The patient or attending physician requests that the patient be withdrawn from the study.
- Enrollment in any other clinical trial involving an off-label use of an investigational drug or device or enrollment in any other type of medical research judged not to be scientifically or medically compatible with this study.
- The patient, for any reason, requires treatment with another therapeutic agent that has been demonstrated to be effective for treatment of the study indication. In this case, discontinuation from the study occurs prior to introduction of the new agent.
- The investigator or AROG stops the study or stops the patient's participation in the study for medical, safety, regulatory, or other reasons consistent with applicable laws, regulations, and good clinical practice.

Patients in these circumstances will be followed as per the Study Schedule (appendix IV) and section 11.1.7.

For patients lost to follow-up or undergoing initiation of another drug therapy including allogeneic HSCT, the study schedule will be stopped but patients should be followed for survival data if at all possible.

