The modeling/simulation cycle described above was performed with combined data from two adult studies (19 patients, ARO-BRE-001 (NCT01229644) and 002 (NCT01243346)) and one pediatric study ARO-003 (NCT01393912). This data was used to perform distribution of the BSA-normalized crenolanib pharmacokinetic parameters and the expected distribution of BSA in an adult population to perform 1,000 Monte Carlo simulations for each regimen. In figure 8.1, the shaded regions represent the 95% CIs for each simulation. The patients' dosing interval is considered to be every eight hours. Although the drug would be administered three times a day on a "TID" schedule, it is important to understand that the simulation was performed using an every eight hour dosing schedule and every attempt should be made to dose the drug on this schedule.

[figure not shown]

Figure 8.1. The PK simulation for TID (median +/- SD) plotted based on a simulation of data from 19 adult patients and pediatric patients.

The serum PK results of the 16 AML patients enrolled to date at 100mg TID across two clinical studies show that fifteen have cycle 1 day 15 average trough levels of 444nM (standard error ±15nM), below the theoretical target of 680nM required to inhibit FLT3 signaling in bone marrow. In addition, the Pk data suggest that crenolanib is slowly absorbed with a t-max of 2-4 hours and mean terminal half-life ranging from 8.6-9.5 hours. This suggests the currently administered crenolanib dose of 100mg TID (protocol v3) is insufficient to achieve adequate sustained inhibition of FLT3 kinase activity. As of May 2013, of the 16 patients enrolled across two clinical studies, 4 have achieved a CR (1CR/3CRi) with 6 others having some short lived reduction in blast cells in either blood or marrow and another 4 patients showing no response. In the 6 patients with blast decrease, blast reduction occurred by 21 days but was not sustained. These results suggest pharmacologic failure for most patients at this initially selected dose of 300mg/day (100mg/TID). In addition, AML patients over 85kg did not achieve sustained responses and are potentially underdosed on a flat-dose schedule.

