In contrast to the flat mg/day dosing schedule currently given on this trial under protocol v3, an ongoing phase I trial (NCT01393912) in pediatric patients with malignant brainstem glioma has treated 49 patients at four escalating dose levels of single agent using mg/m2/day dosing. Nine patients have received crenolanib at 220mg/m2 QD as a single daily dose. Six out of these 9 patients were on study drug for the DLT period of 28 days. Two patients experienced DLT of transaminase elevations and stopped crenolanib therapy with subsequent resolution of abnormal

labs. Thus in the pediatric population 220mg/m2 given as one single daily dose approaches MTD but otherwise yields no other significant toxicities.

Because a single daily dose achieves higher peak concentrations of drug, we have hypothesized that once daily dosing is associated more commonly with potential toxicities such as LFT elevations; and a BID or TID schedule will lower peak drug concentrations potentially allowing more sustained dosing, less toxicity and improved pharmacokinetic profiles. At the current 100mg TID dose prescribed in this trial (protocol version 31) no substantial drug related toxicities have been observed. The most common drug related adverse events (AEs) reported as grade 1 or 2 nausea and vomiting. Two patients required dose reductions for Grade 3 and 4 transaminitis, which resolved once drug was held. Both were on two CYP3A4 inhibitors which may interfere with drug metabolism. Both patients tolerated 80 mg TID without transaminitis. A crenolanib dose of 200mg/m²/day given as a TID schedule is postulated to result in a lower peak drug concentration and potential toxicities but provide adequate sustained dosing levels to reduce pharmacologic failure. Pharmacokinetic data will continue to be collected.

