There will be one level dose escalation allowed for patients who do not experience grade 3 or 4 toxicity and who have no response based on investigator evaluation.

Table 8.2: Dose escalation guidance

Dose level	Crenolanib dosing
0	$200 \text{ mg/m}^2/\text{day}$
+1	$220 \text{ mg/m}^2/\text{day}$

Dose escalation can occur as early as cycle 1 day 15.

Protocol: ARO-004

Counting Cycle Days: If drug is held or a dose is missed, the missed/held dose should not be made up. Dosing will resume with the next scheduled dose. The patient should enter in the diary the doses as missed. If drug is held or missed for a day or more, the cycle should continue as if uninterrupted. Counting days of a cycle should be ongoing without disruption. The start of cycle 1 is denoted by the ingestion of study drug. The scheduled procedures/visits should comply with the study calendar regardless of amount of study drug administered in a 28 day cycle.

8.7.1 Dose Reductions for Crenolanib for Non-hematologic Toxicities During Reinduction and Post Allogeneic Transplant

Toxicities will be graded using the NCI CTCAE, Version 4.03 (Appendix VI).

For patients receiving crenolanib for reinduction therapy: Dose reductions for non-hematologic toxicities except nausea, vomiting, and diarrhea due to crenolanib will be done according to the schema in Table 8.3. Dose reductions are summarized in Table 8.4 and reductions below 160mg/m²/day will lead to withdrawal from the study drug, in which case the patient will stop taking crenolanib, but will still be followed for outcomes as outlined in 8.12.

Table 8.3. Based on NCI CTCAE v4.03, Crenolanib Dose Reduction for Non Hematologic Toxicities Except Nausea, Vomiting, and Diarrhea related to study drug. Use toxicity grade at time of start of next planned cycle. Reassessment may be performed weekly to determine when to restart drug or dose modify. A 28-day deferment window is allowed to assess toxicities.

Toxicity (NCI Criteria)	Dose modification for patients taking crenolanib as reinduction
Grade 1 or 2	No dose modification
Clinically significant or persistent grade 2 despite optimal therapy	Hold drug until toxicity resolves to grade 1 or less. Restart drug at same dose level (Table 8.4).
Grade 3 or 4	Hold drug until toxicity resolves to grade 1 or less. Restart drug at next-lower_dose level (Table 8.4).

Table 8.4. Dose levels of Crenolanib During Reinduction

Dose Level	Crenolanib Daily Dose
Baseline	200mg/m ² /day

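### Does the 33% accrual stop have no event to count because Section 8.7 never uses the term unacceptable toxicity?

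*Combined protocol and SAP*

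**What the plan says.** The accrual rule appears twice. Section 10.3.7 states that "if at any time unacceptable toxicity is encountered in more than 33% of patients the accrual will stop and lower doses may be investigated". The Statistical Methods part of the Synopsis has the same rule: "if at any time unacceptable toxicity is encountered in more than 33% of patients, the accrual will stop".

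The term occurs once more, in the Section 6.3.1 list of reasons for taking a patient off study drug while continuing survival follow-up: "The patient experiences unacceptable toxicity as defined in Section 8.7". Section 8.7 itself does not use the words. It sets out holds, reductions and withdrawals. In reinduction, for example, a reduction below 160 mg/m²/day "will lead to withdrawal from the study drug".

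Section 10.3 mentions binomial tests for response and toxicity and points to Section 11. Section 11 covers event definitions, attribution and reporting, and contains no test. Section 10.2, Toxicity Evaluation, gives no criterion.

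On earlier experience, Section 8.6 refers to "The serum PK results of the 16 AML patients enrolled to date at 100mg TID across two clinical studies". At that dose it says that "no substantial drug related toxicities have been observed", and then reports: "Two patients required dose reductions for Grade 3 and 4 transaminitis, which resolved once drug was held". It adds: "Both patients tolerated 80 mg TID without transaminitis".

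**The concern.** This is the only numerical toxicity limit on accrual, and the place said to define its event does not name one. Section 8.7 contains both prompt events (grade 3 or 4, answered by hold and reduction) and late ones (withdrawal). The two transaminitis cases count as two events under the first kind and as none under the second.

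Two consequences would follow if the ambiguity were open. With a prompt event, one affected patient among the first three stops accrual. With a late event, newly started patients enter the denominator before they can contribute to the numerator, so fast enrolment could outrun the limit. The missing test in Section 11 suggests that the toxicity plan was left unfinished.

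**Working it through.** **1. Which provisions fit the term?** Section 6.3.1 makes unacceptable toxicity a reason to stop drug. The Section 8.7 provisions compare with that use as follows.

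| Provision | Place | Effect on treatment | Fits Section 6.3.1? |
|---|---|---|---|
| Grade 3 or 4 non-hematologic toxicity | Tables 8.3, 8.5 | hold, restart one level lower | no |
| Persistent or clinically significant grade 2 | Tables 8.3, 8.5 | hold, restart at same level | no |
| Hematologic guidance in reinduction | 8.7.2 | continue, hold or reduce | no |
| Reduction needed below 160 mg/m²/day, reinduction | 8.7.1 | withdrawn from drug | yes |
| Reduction needed below 140 mg/m²/day, post-transplant | 8.7.1 | drug stopped | yes |
| Total hold of 56 days or more | 8.7.4 | discontinued | yes |

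If grade 3 or 4 toxicity were the event, Section 6.3.1 would stop the patients whom Tables 8.3 and 8.5 restart. The withdrawal provisions produce no such conflict. The two transaminitis patients resumed at 80 mg TID, so on this reading they are zero events, which agrees with the description of that record in Section 8.6.

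**2. Does the choice change a decision on the reported data?** Section 8.6 gives 2 cases and 16 patients across two studies; this trial's share is not stated.

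- Withdrawal reading: 0/16 = 0%.
- Grade 3 or 4 reading: 2/16 = 12.5%. With 14 patients it would be 2/14 = 14.3%.
- Two events exceed 33% only if n < 2/0.33 = 6.06, that is, 6 patients or fewer (2/6 = 33.3%; 2/7 = 28.6%).

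**3. What the literal rule does with prompt events.** Halt at the first n with x > 0.33n: 1 of 1–3, 2 of 4–6, 3 of 7–9, 4 of 10–12, 5 of 13–15. The chance of a halt by patient 14, by exact patient-by-patient recursion, is:

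| Assumed true rate | 10% | 20% | 30% | 40% |
|---|---|---|---|---|
| Halt by patient 14 | 29.9% | 57.8% | 79.4% | 92.3% |

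These figures follow from the threshold and from checking at any time. Printing the counts or moving the rule to Section 10.2 would alter none of them.

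**4. Can accrual outrun a late event?** The pace is not given, but the Synopsis gives a study length of 3 years, 14 evaluable subjects and at most 365 days of treatment. Assume accrual fills between 2 years (3 years less one year of treatment) and the full 3 years:

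- 3 years: 14 / (1095/56) = 0.72 entries per 56 days.
- 2 years: 14 / (730/56) = 1.07 entries per 56 days.

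Take an assumed true rate of 40%, outcomes known 56 days after entry, all treated patients in the denominator, and a check before each of entries 2 to 14:

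| Entries per 56 days | 0.72 | 1.07 | 2 | 4 | 8 |
|---|---|---|---|---|---|
| Halt before patient 14 enters | 92% | 86% | 86% | 62% | 9% |

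Only entries per delay matter. An 84-day delay with two-year accrual is 14 / (730/84) = 1.61 entries per delay, which leaves two patients unresolved at each check, as at 1.07 and 2, and so gives the same 86%. The weak figures need all 14 patients within 14/4 × 8 = 28 weeks or 14/8 × 8 = 14 weeks.

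**5. Does the test named in Section 10.3 conflict with the rule?** No null rate or level is stated. Taking 33% as the null, with 14 patients: P(X ≥ 5) = 0.514, P(X ≥ 8) = 0.054, P(X ≥ 9) = 0.016. A one-sided 5% test would need 9 of 14, while the rule stops accrual at 5 of 14. A stopping limit during conduct and a test at analysis answer different questions, and nothing in the text makes the rule depend on the test.

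**The case for a change.** The strongest case for a change is that a stopping rule should be operable from the page. The cross-reference in Section 6.3.1 finds no labelled definition. Even on the withdrawal reading, two dose floors and a hold limit remain, and they differ before and after transplant. The rule does not say whether patients enrolled under version 3 count. That matters: if this trial had, hypothetically, six such patients with no event, the halt probability over the next 14 at a true 40% with prompt events would fall from 92% to 42%. Version 4 also introduces dosing by body surface area, so the brake on accrual deserves care.

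The missing label and the empty Section 11 reference stand. The rest has less force. The two floors and the hold limit are not rivals: each is a way for treatment to end, and a patient who reaches any of them has stopped drug. Sections 7.1 and 10.3.9 already take all patients as the toxicity population, which supplies a default denominator.

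The alternative of leaving out version 3 patients who stay on 100 mg TID is not clearly better. Section 8.7 sets the smallest body surface area at 1.5 m², and 1.5 × 200 = 300 mg/day, the same daily total as 3 × 100 mg. Section 8.7 also ties escalation of version 3 patients to absence of grade 3 or 4 toxicity, so counting only those who move up would favor tolerant patients. Finally, the rule is not the only protection: individual hold and withdrawal rules apply throughout, and Section 6.3.3 lets the site review board or the sponsor stop the study.

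**Conclusion.** No change to the plan follows. The term is undefined where Section 6.3.1 says it is defined, and the Section 11 reference is a clerical slip. The way Section 6.3.1 uses the term points to the provisions that end treatment, and a team applying the rule can record that reading before it counts. Whether those provisions are the right clinical threshold is for the sponsor; this note says only how the text reads.

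The choice of reading changes no decision on the 16 reported patients (0% or 12.5%, against 33%). It could do so only if this trial's own share were six or fewer and grade 3 or 4 cases counted. Late events leave an 86% to 92% chance of halting at a true 40%, assuming accrual over two to three years and a 56-day delay. The severe losses require enrolment within 14 to 28 weeks. The 30% chance of a halt at a true 10% rate belongs to the grade 3 or 4 reading with events known at once; it is the price of a strict limit checked at every patient, and a label would not alter it. All halt probabilities rest on assumed true rates.

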10.3.9 Safety Analyses

All patients will be evaluable for safety. Adverse events that occur after a patient is entered (signs informed consent), but before the patient receives study drug, will not be recorded on the CRF unless the investigator believes that the events may have been caused by a protocol procedure. Safety analyses will include summaries of the incidence of adverse events by maximum CTCAE grade (version 4.03; NCI 2010) that occur during the study treatment period or within 30 days of the last dose of study treatment, regardless of causality or relatedness to study drug. The safety-related outcomes that will be summarized include:

- Adverse events,
- TEAEs,
- SAEs,
- Deaths.
- Discontinuations due to adverse events,
- Extent of exposure to study drug treatment,
- Hospitalizations,
- Use of key concomitant medications (for example, antipruritus medication).

Analyses for data with discrete dates (for example, deaths and concomitant medications) will be performed through 30 days after the patient has been discontinued from study treatment. Adverse events will also be analyzed in this time frame. After 30-day post-discontinuation follow-up, only those SAEs that are thought to be related to study treatment or protocol procedure should be reported immediately to AROG or its designee. For these events, the patient must be followed until the event has resolved or stabilized.

